**8.0 Study Endpoints:**

**8.1** The primary study endpoint will be the completion of all analysis of the Aims. A secondary study endpoint will be when all patient interviews are completed (n=700).

Table 4. Study Measures and Outcomes		Interview Timepoint				
Variable	Instrument(s) or Measure(s)	BL	6w	6m	12m	18m
Covariates		IP			IP	
Socio-demographics, patient characteristics	Age, sex, race/ethnicity, education, income, language, country of origin, time in US, others	■				
Health status (physical, mental)	Promis – anxiety & depression, global, physical	■				
Cognitive status	BTACT	■			■	
Social support	TSS; Medication Support Survey	■			■	
Health literacy	NVS, Chew	■			■	
Patient activation	CHAI	■			■	
Regimen characteristics	MRCI, drug class, cost	■		■	■	■
System Process Outcomes						
Receipt of UMS materials	Receipt of UMS (yes/no)		■	■	■	■
Medication reconciliation	Updates to medical/pharmacy records				■	
Receipt of SMS text reminders	Receipt of SMS (yes/no), satisfaction		■	■	■	■
Completion of assessment	Completion of assessment, satisfaction		■		■	
Clinic follow-up	Did clinic follow up on concerns		■		■	
Intervention impact on clinic practice	Qualitative interview with clinic staff					
Patient Effectiveness Outcomes						
Medication adherence	ASK-12, 24hr recall	■	■	■	■	■
	Pill Count	■		■		
	Proportion of Days Covered, Tacrolimus Levels			■	■	■
Treatment knowledge	General Rx knowledge, Demonstrated use, Consolidation	■	■	■	■	■
Quality of Life	PROMIS (physical, anx, dep, global)					
Clinical outcomes	Transplant related: eGFR, re-hospitalization, IFTA, acute rejection, toxicity, infection					
	Systolic blood pressure, Hemoglobin H1AC	■		■	■	
Cost Outcomes						
Programming maintenance costs for EHR	Printer ink, paper, staff time					
Running UMS technologies						
SMS monthly costs						

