### **8.4 Effectiveness Outcomes.** We will collect data on an array of knowledge, behavioral, and clinical outcomes.

Medication Adherence. Adherence will be measured using: 1) the Ask-12 Scale that assesses general medication attitudes and beliefs, 2) patient self-report of how many pills and how often each medicine was taken over the last 24 hours; 3) in-person and/or phone pill count using established guidelines employed by our team [R01HS00167; PI [name]]; 4) a biologic measure using tacrolimus levels. For 24 hour recall, correct dosing will be measured as yes/no per drug, having properly shown dose (# pills), spacing (hours between doses), frequency (times per day), and total pills/day. For pill count, we will assess adherence within drug calls. If a patient fills a prescription for a drug in a class and then switches to another drug within the same class, all prescriptions will be summed in the numerator. Adherence will be treated both continuously and dichotomously (adherent  $\geq 80\%$ ).

Biologic Measure. Medication adherence to IS medications will also be assessed by computing the standard deviation (SD) of a series of tacrolimus levels obtained for routine monitoring using validated methods. Standard clinical practice at participating centers includes routine monitoring of tacrolimus levels. Tacrolimus levels obtained during acute illness will not be included in the SD calculation. This schedule should result in >30 levels in the first 6 months post KT, 12 levels in months 6-12, 6 levels in months 13-18, 6 levels in months 19-24; and 6-8 levels per year after the second year. Laboratory methods for measurement of whole blood levels are standardized, which should reduce variability between sites. SD calculations will be made using  $\geq 4$  levels obtained over 6 months based on availability. A higher SD indicates more variability between individual measures, and is highly correlated with less stable medication intake (non-adherence) and graft rejection. A SD of the mean levels of  $\geq 2.5$  will be indicative of non-adherence. This biologic measure of adherence will be calculated at 6 month intervals to correspond to interviews.

Composite adherence measure. Each individual measure of adherence has advantages and limitations, thus we will use multiple measures as recommended by experts. Maximum

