## 9.9 Research Procedures

Research activities will include a baseline interview, and follow-up interviews at 6 weeks, 6 months, 12 months, 18 months and 24 months. The baseline and either the 12 month or the 18 month interview will be conducted in-person\*, while the remaining interviews will be conducted via phone. To facilitate the geographical diversity of KT patients at the Mayo Clinic, measures used in the baseline and 12 month interview can be administered in-person or via phone. If a pill count needs to be completed over the phone, a pill count tray will be sent to the participant prior to the scheduled interview.

\*If the 12-month interview cannot be done in person due to the timing of clinic visits, it will be done over the phone and we will attempt to do the 18 month interview in person.

**Pilot Testing and Refinement of Study Procedures.** We will pilot test our strategy and study protocol, including the evaluation battery and patient materials, among 10 KT recipients per site who meet established patient eligibility criteria. Cognitive interviews (~45 min.) will be conducted to finalize and/or refine all study materials. We will 1) obtain average completion times for the interview, 2) elicit patient comprehension of the interview and intervention components. Necessary modifications will be made prior to full-scale implementation.

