**Follow-up Interviews.** At Northwestern, an automatic reminder function built into Microsoft Access will alert RAs when to schedule follow-up encounters (6 weeks, 6, 12, 18, and 24 month interviews). Northwestern will send Mayo a weekly list of ID numbers and dates, prioritizing patients to schedule based on their windows. Each interview will take approximately 45-60 minutes, and subjects will receive \$30 for baseline, 6 month and 12 month interviews, and \$50 for the 18 month interview (total \$140 compensation; none for 6 week or 24 month 20 minute phone interview).

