**11.0 Data and Specimen Management:**

**11.1 Analysis Plan.**

All analyses will be performed in SAS v9.4 (SAS Institute, Cary, NC). [name] will perform analyses under the direct supervision of Drs. [name], [name] and [name]. Drs. [name] and [name] will also provide guidance.

Aim 1.

The proposed trial uses a 1:1 randomized design that assigns patients to TAKE IT or usual care within each cohort. We will accrue approximately 700 patients (350 de novo, 350 established) anticipating 90% retention in the de novo cohort (85% established) for follow-up at 1 year, leaving a minimum 525 patients for primary analyses. High retention will be supported through close follow-up, mailed reminders, birthday cards, and a newsletter. Given the clinical follow-up necessary for KT recipients, we are confident we will achieve this goal.

Regimen adherence at one year is the primary outcome of interest for Aim 1, with Rx knowledge and individual adherence measures also of primary interest. Secondary outcomes include quality of life (PROMIS outcomes and FKSI) and the clinical outcomes of change in eGFR, and any transplant-related re-hospitalization. Blood pressure control in those taking anti-hypertensive medications will also be examined. Relationships between

adherence and potential confounders (age, comorbidity, cognitive ability, regimen complexity, internet use, dose of intervention, etc.) will also be examined. For all outcomes, we will use generalized linear models (GLMs), adjusted for confounders and study site, specifying the logit link function for binary outcomes and identity link for continuous outcomes (quality of life, change in eGFR, SBP). Treatment group will be the independent variable of primary interest, with usual care specified as reference group. We will also include time since transplant at baseline (in months), baseline value of the outcome, and any potential confounding covariates noted in bivariate analysis. For outcomes measured per medication, a generalized estimating equation (GEE) approach will be employed to adjust standard errors for within-patient correlation. Should TAKE IT have an effect on outcomes, secondary analyses will examine if any of the potential confounders considered exhibit any effect modification.

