### Aim 2.

Generalized linear mixed models (GLMMs) will be used to examine intervention effects over the course of the study. Link functions will be included as described above for the GLM models. Adherence concerns may differ in the two cohorts, thus separate models will be employed for each cohort (de novo, established). Treatment group will be the independent variable of primary interest, modeled as a fixed effect with the usual care group specified as reference group. We will also include fixed effects for site (NU, Mayo), time since transplant (in months), and potential confounding covariates noted in bivariate analyses. Random participant effects for each participant will be included to account for repeated measurements nested within each participant (assuming a compound symmetry, although we will fit autoregressive structures as well, comparing fit using AIC and BIC criterion). Outcomes recorded at each interview will be analyzed by visit whereas adherence measured by tacrolimus levels, along with blood pressure control will be analyzed in 6-month intervals as described above. A time-since-transplant-by-arm interaction term will be included to examine if outcome trajectories/slopes over time differ by study arm. Since prescription knowledge and adherence will be assessed for each medication, 2-level GLMM will be used for these outcomes with medications nested in participants. For  $\Delta$  eGFR and re-hospitalization outcomes, GLM models will be used since outcomes over 2 years are summarized in a single measurement. In the de novo cohort, change in eGFR from transplant to 2 years post-transplant and # hospitalizations (any hospitalization, if rare) within 2 years post-transplant will be modeled. For the established cohort, the time period for the both measures will span from transplant to 2-year study visit. It is possible those who do not complete the 2-year visit will differ in important characteristics (e.g. cognition, comorbidity), which could bias results. We will use collected data at prior interviews to understand the extent that individuals who complete follow-up differ from those who do not. If differences are found, pattern-mixture models will be employed by classifying participants' drop-out type or pattern (e.g. completed, refused, lost to follow up, death). This variable will then be added to mixed effects models to account for differences.

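### Aim 2's mixed models judge persistence of the repeated outcomes by one linear arm-by-time slope, with no named 24-month arm contrast and no stated role for the baseline visit

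*Combined protocol and SAP*

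**What the plan says.** Section 1.1 sets Aim 2 as the question whether effects persist over 2 years. Section 11.1, Aim 2, answers it for repeated outcomes with generalized linear mixed models fitted separately in the de novo and established cohorts. Arm is a fixed effect, and the plan adds "We will also include fixed effects for site (NU, Mayo), time since transplant (in months") and confounders. The time-related arm term is: "A time-since-transplant-by-arm interaction term will be included to examine if outcome trajectories/slopes over time differ by study arm".

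On the unit of analysis it says "Outcomes recorded at each interview will be analyzed by visit", with tacrolimus-based adherence and blood pressure control taken in 6-month intervals. Section 9.9 counts baseline among the interviews: "Research activities will include a baseline interview, and follow-up interviews at 6 weeks, 6 months, 12 months, 18 months and 24 months".

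Aim 1, by contrast, states how baseline enters: "We will also include time since transplant at baseline (in months), baseline value of the outcome". Aim 2 has no such statement. It does give single-measurement 2-year models for change in eGFR and re-hospitalization, and the one-year comparison belongs to Aim 1.

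**The concern.** Persistence is a question about the size of the arm difference late in follow-up. A slope answers a different question: whether the difference changes along a straight line. For the repeated outcomes the plan names only the slope and gives no rule for reading it as persistence or loss.

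The reading also depends on an unstated choice. Treating baseline as an outcome row is natural, because outcomes are analysed by visit and baseline is an interview. But there is no treatment effect at baseline, so the onset of benefit between baseline and 6 weeks is absorbed into the slope. A non-significant interaction could then be reported as persistence when half the effect has gone, and a stable effect could be reported as growing.

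**Working it through.** **The plan's own figures.** The power section covers one-year comparisons only. With a two-sided 5% test and pooled variance, 45% v 34% at 305 per arm gives 79.5% power. With n multiplied by 0.8 (R-squared 0.2) it gives 70%. For the established cohort, 50% v 35% at 170 per arm gives 80%. These agree with the plan. It states no power for the Aim 2 slope.

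**Inputs.** From the documents: interviews at 0, 1.5, 6, 12, 18 and 24 months; compound symmetry as the default; 170 per arm (Table 5, established, a one-year number). Assumed: effect −0.30 SD (Table 5's 15.0 points at 50% is 0.15/0.5 = 0.30 SD), zero at baseline and full from 6 weeks unless it fades; within-patient correlation ρ = 0.5; entry spread evenly over 6–24 months after transplant (variance 18²/12 = 27). Negative means benefit.

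**Formula.** Time in the model is entry plus visit month t. With m visits, the information per patient on the slope is W = Σ(t − t̄)²/(1 − ρ) within patients and B = m × 27/(1 + (m − 1)ρ) between patients. The effect depends on visit and not on entry, so

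expected slope = [W/(W + B)] × Σ(t − t̄)e(t)/Σ(t − t̄)², with SE = √(2/[170(W + B)]).

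**Baseline as a row, six interviews.** t̄ = 10.25 and Σ(t − t̄)² = 451.875. W = 903.75, B = 162/3.5 = 46.3, weight 0.951, SE 0.00352.

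| True course | Σ(t − t̄)e/Σ(t − t̄)², per unit effect | Slope per month | Significant |
|---|---|---|---|
| Lasts | 10.25/451.875 = 0.0227 | −0.0065 | 45% |
| Halves linearly, 6 weeks to month 24 | 0.55/451.875 = 0.0012 | −0.0004 | 5% |
| Lost linearly, 6 weeks to month 24 | −9.15/451.875 = −0.0202 | +0.0058 | 38% |
| Lost linearly from randomisation | −8.58/451.875 = −0.0190 | +0.0054 | 34% |
| Held to month 12, lost by 24 | −7.375/451.875 = −0.0163 | +0.0047 | 26% |

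First row in full: 0.951 × 0.0227 × (−0.30) = −0.0065; 0.0065/0.00352 = 1.84; Φ(1.84 − 1.96) = 45%.

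**Sensitivity.** For ρ from 0.3 to 0.7 a lasting effect is significant in 33–67% of trials and a halved one in about 5%. Under AR(1) correlation of 0.5–0.8 the lasting figure is 20–22%. De novo (135 per arm): lasting −0.0068 (39%), halved about zero (5%). A random-intercept logistic simulation on Table 5's established-cohort rates gave 39% lasting and 5–6% halved.

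**Baseline as a row, no 6-week value** (0, 6, 12, 18, 24). Σ(t − t̄)² = 360, weight 720/765 = 0.941. The halved effect gives 0.941 × (4.4/360) × (−0.30), about −0.0034 to −0.0035 depending on the shape of the decline. This is no longer near zero and points towards growth.

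**No baseline row** (1.5 to 24). t̄ = 12.3, Σ(t − t̄)² = 325.8, W = 651.6, B = 45, weight 0.935, SE 0.00411.
- Lasting: slope 0 (5%), the same as no effect at all.
- Linear fade from randomisation: 0.935 × (1/24) × 0.30 = +0.0117, 81% power.
- Held to month 12, then lost: 0.935 × (14.55/325.8) × 0.30 = +0.0125. The mean effect is −0.30 × 3.5/5 = −0.21, so the line gives −0.21 at month 12 and −0.21 + 11.7 × 0.0125 = −0.06 at month 24. True values are −0.30 and 0: the line shows a loss of 0.15 out of 0.30.

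**The case against.** The strongest reply is that the plan never says baseline is an outcome row. Without it the slope is unbiased for a lasting effect and tests a linear fade well. That stands, so the tilted slope is a conditional finding. The missing level estimate and the half-recovered late loss do not depend on it.

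Second, even with a baseline row the fitted line ranks the cases correctly at month 24: −0.34 lasting, −0.19 halved, −0.11 held then lost, −0.05 lost linearly (true −0.30, −0.15, 0, 0). That is a fair point, and naming the 24-month contrast would remove much of the problem. The plan does not name it.

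Several stronger readings are tempting but unsupported:
- A reader might infer that the slope cannot tell a lasting effect from a lost one. The two have opposite signs, so the signed estimate separates them, and the rates differ (45% v 26–38%). The halved case is the one it fails to identify.
- A reader might suppose that the line is forced through zero at baseline. The arm term is free: for a lasting effect the fitted baseline difference is −0.25 + 10.25 × 0.0065 = −0.18.
- A reader might attach a fixed share of lost effect to a flat slope. That share changes with the visits included, as the run without the 6-week value shows.
- A reader might conclude that the trial has no 12-month or 2-year comparison. Aim 1 has the former, and eGFR change and re-hospitalization have the latter.

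**Conclusion.** The concern holds for the repeated outcomes in the Aim 2 mixed models. Persistence is tested only through one linear slope, no 24-month contrast is named, and the role of baseline is unstated. If baseline is a row and all six interviews are used, a lasting effect looks like growth (−0.0065 per month, 45% significant) and a halved effect looks like persistence (about zero, 5%). If baseline is not a row, the slope is sound for a lasting effect or a linear fade, but it cannot separate lasting from absent and recovers about half of a late loss.

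The figures rest on the assumed effect size, correlation, entry spread and shapes of loss. They concern participant-level outcomes; the nesting of medications within patients was not modelled. The false slope does not reach the measures in the Table 4 row "Proportion of Days Covered, Tacrolimus Levels", which as read has no baseline mark; section 8.4 says of the tacrolimus measure: "This biologic measure of adherence will be calculated at 6 month intervals to correspond to interviews". This should be fixed, but it does not touch the trial's primary one-year result.

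**What to change.** In the Aim 2 mixed models only:
- Model study visit since randomisation as a categorical factor with arm-by-visit terms.
- Adjust for the baseline outcome, or constrain it equal across arms, where it is measured. Keep months since transplant at baseline as a covariate.
- Name the 24-month arm contrast as the lead persistence estimate, shown beside the 12-month contrast.
- List what the month-24 call collects and use the last scheduled visit for anything it omits. Table 4 as read has no 24-month column, and section 9.9 describes a short call with no payment ("none for 6 week or 24 month 20 minute phone interview").
- Keep an arm-by-time slope timed from randomisation, without the baseline visit, as a supporting test.

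The cost is SAP wording and that list; no new data are needed for measures already collected at month 24. There is a price in precision. With an assumed further 0–20% loss after month 12, the SE of the 24-month contrast is 0.094–0.103 SD with baseline constrained (0.096–0.099 from the line), and 0.108–0.117 where there is no baseline (0.097–0.104 from the line). The 24-minus-12-month change is weaker: SE 0.108–0.117, with 25–28% power for a linear fade against 75–81% for the slope without baseline. That is why the slope should stay. For an effect held to month 12 and then lost, the change has 73–79% power, against 17–26% for a slope that includes baseline and 78–86% for one that does not.

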#### **2.4 Preliminary Data: Prevalence of Transplant Adherence and Barriers.**

We recently conducted interviews with 99 KT recipients at Northwestern and Emory Universities. 24% of participants had limited literacy. Patients were taking an average of 11 (SD=4) medications; one third (32%) had a medication change in the past month. 1 in 4 KT recipients could not demonstrate proper regimen use for IS regimens and 35% were poorly adherent based on self-report or by tacrolimus level standard deviation. In multivariable analyses, fewer months since transplant and limited literacy were associated with poor adherence (all  $p < 0.05$ ). In multivariable models, patients over 65 (OR 2.45, 95%CI 1.20-4.98), non-white race (OR 2.83, 95% CI 1.54-5.20), demonstrating improper regimen use (OR 1.15, 95% CI 1.01-1.30) and inadequate adherence (OR 2.10, 95%CI 1.10-4.01) had a higher post-transplant hospitalization risk.

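### The Aim 2 two-level model for per-medication outcomes has no participant-by-visit effect, so its time-by-arm standard errors can be wrong, and too small under one natural reading

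*Combined protocol and SAP*

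**What the plan says.** The relevant text is the Aim 2 part of section 11.1.

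- For the mixed models in general: "Random participant effects for each participant will be included to account for repeated measurements nested within each participant". A parenthesis adds the covariance structure: "assuming a compound symmetry, although we will fit autoregressive structures as well, comparing fit using AIC and BIC criterion".
- Unit of time: "Outcomes recorded at each interview will be analyzed by visit".
- Trajectory term: "A time-since-transplant-by-arm interaction term will be included to examine if outcome trajectories/slopes over time differ by study arm".
- For prescription knowledge and adherence assessed on each drug: "2-level GLMM will be used for these outcomes with medications nested in participants".

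Section 8.4 makes one of these outcomes binary at drug level: "For 24 hour recall, correct dosing will be measured as yes/no per drug". Section 2.4 gives the number of drugs: "Patients were taking an average of 11 (SD=4) medications". Section 9.9 schedules interviews at baseline, 6 weeks, and 6, 12, 18 and 24 months.

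For Aim 1 the plan covers the clustering of drugs within a patient: "For outcomes measured per medication, a generalized estimating equation (GEE) approach will be employed to adjust standard errors for within-patient correlation". Aim 2 names no visit-within-participant effect, no random slope and no robust standard errors. It does not say whether the compound-symmetry or autoregressive structure carries over to the per-medication model.

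**The concern.** The per-medication data are drugs crossed with visits within participants. Two levels cannot describe that. Answers given at one interview share a single sitting, one 24-hour recall window and one interview mode (in person or by phone), so one disrupted day can affect many drugs at once.

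Time changes only from visit to visit, so the precision of a time-by-arm contrast depends heavily on this shared visit component. A model without it treats some 11 same-day answers as separate evidence about change, given the effects it does include. Compound symmetry generated by a participant effect does not help: it gives two drugs at the same visit the same correlation as two drugs at different visits.

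At stake is the reported precision of the trajectory comparison for per-drug knowledge and adherence. Persistence of effects over two years is a named aim of the trial.

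**Working it through.** **The plan's own figure.** The documents state no standard error, variance component or power for the Aim 2 term. The nearest figure is in Table 5: a detectable difference in non-adherence of 11.0 points (45% in usual care, 305 per arm, 80% power, 5% error). A two-proportion calculation gives 11.07 points, and 79.5% power at 11 points. That is a single-time comparison with one value per patient, so it does not bear on this point.

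**Inputs.** m = 11 drugs (section 2.4). Split the within-participant variance into shares: v (visit, common to all drugs that day), c (stable drug within participant) and e = 1 − v − c. Both v and c are assumptions.

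**Reading A: participant intercept only** (balanced linear approximation). In a slope contrast the stable drug effect cancels, so each visit mean has true variance v + e/m. The model puts all within-participant variance in the residual and reports 1/m. Hence

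(true SE / reported SE)² = m·v + e = 1 + (m − 1)v − c.

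Actual type I error = 2[1 − Φ(1.96 / ratio)]. With m = 11 and c = 0:

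| v | squared ratio | SE ratio | actual error |
|---|---|---|---|
| 2% | 1 + 10(0.02) = 1.20 | 1.10 | 7.4% |
| 5% | 1.50 | 1.22 | 11.0% |
| 10% | 2.00 | 1.41 | 16.6% |

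At one SD either side of the mean number of drugs (m = 7 to 15), the ratio runs from 1.14 to 1.30 at v = 5% and from 1.26 to 1.55 at v = 10%.

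With stable drug variance the ratio falls. At c = 20% it is 1.00, 1.14 and 1.34 for v = 2%, 5% and 10%. At c = 50% it is 0.84 for v = 2% and 1.00 for v = 5%. Reported standard errors are too small only if 10v > c.

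**Reading B: medication within participant also fitted.** The residual now holds v + e = 1 − c, so the reported variance is (1 − c)/m and

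(true SE / reported SE)² = (m·v + e)/(1 − c) = 1 + (m − 1)v/(1 − c).

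This exceeds 1 for every v > 0. At c = 0 it equals the table. At c = 20% and v = 5% it is 1 + 0.5/0.8 = 1.625, a ratio of 1.27.

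**Check with a binary outcome.** A logistic model with a participant intercept only was fitted to simulated data: 270 participants (the de novo number in Table 5), 11 drugs, six visits on study time, participant SD 1.0 on the logit scale, no true time-by-arm effect, 400 runs per setting.

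| visit SD | drug SD | SE ratio | rejection |
|---|---|---|---|
| 0 | 0 | 0.97 | 4.2% |
| 0.3 | 0 | 1.12 | 8.8% |
| 0.5 | 0 | 1.24 | 11.0% |
| 0.8 | 0 | 1.45 | 18.0% |
| 0 | 1.0 | 0.90 | 2.8% |
| 0.3 | 1.0 | 1.00 | 4.5% |
| 0.5 | 1.0 | 1.12 | 9.0% |
| 0.3 | 1.5 | 0.91 | 2.2% |

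Monte Carlo error near 5% is √(0.05 × 0.95/400) = 1.1 points. Both directions appear, as the formula predicts. On the latent scale (residual π²/3 = 3.29), visit SDs of 0.3, 0.5 and 0.8 with no drug effect are shares of 2.7%, 7.1% and 16.3%. The formula then gives 1.13, 1.31 and 1.62, so for larger shares it overstates the effect on a binary outcome.

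**The case against.** The strongest reply is that the plan may already cover this. The two-level sentence follows a general specification that offers compound symmetry or autoregressive structures for repeated measurements, and it can be read as adding drugs to that. If such a structure were placed on visit-indexed participant effects, correlation shared by drugs at one visit would be modelled. The text does not say so, and a participant-effect compound symmetry would not do it. What stands is that part of the problem is ambiguity.

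A reader might infer that the standard errors are certain to be too small. The documents do not support that. The same two-level wording may also omit the stable drug effect, which pulls the other way. The same drugs may be followed over several interviews, so a sizeable c is plausible.

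A reader might also obtain larger ratios, 1.11, 1.26 and 1.49 at 2%, 5% and 10%, from 1 + 11v/(1 − v). That takes the omitted visit variance out of the fitted residual, whereas the fitted model leaves it there.

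Finally, a reader might take the time-by-arm term as the only Aim 2 test, or think the primary result is at risk. Aim 2 names treatment group as the variable of main interest and includes the interaction to compare trajectories. The primary outcome, adherence at one year, belongs to Aim 1. Outcomes not analysed per drug, such as tacrolimus variability, quality of life, blood pressure, eGFR change and re-hospitalization, are outside this point.

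**Conclusion.** The point holds within limits. As written, the per-medication Aim 2 model lacks a participant-by-visit component, and its time-by-arm standard errors cannot be relied on. With medication within participant fitted, they are too small for any shared visit variance. With a participant intercept only, their validity depends on two omissions cancelling, that is, on 10v being close to c.

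The sizes in the first table (ratios 1.10 to 1.41, actual error about 7% to 17%) rest on 11 drugs, c = 0, visit shares of 2% to 10% and a balanced linear approximation. None of the variance shares comes from the documents. The Aim 1 one-year analysis and Table 5 are unaffected. This should be settled before the Aim 2 analysis.

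**What to change.** State the per-medication Aim 2 model in full, in one of two ways:

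1. Random effects for participant, participant-by-visit and medication within participant. This removes both sources of error and keeps the mixed model, so the planned pattern-mixture approach to drop-out still applies.
2. The planned mixed model with participant-clustered robust (sandwich) standard errors, which allow for any remaining within-participant correlation.

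In either case, say whether the compound-symmetry or autoregressive structure applies to visit-indexed participant effects in this model.

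Moving Aim 2 to GEE, as in Aim 1, would also protect the standard errors. It is a larger change: it replaces subject-specific effects with population-average ones, and unweighted GEE needs stronger missing-data assumptions in an analysis where the plan already expects drop-out to matter.

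The cost is a sentence or two in the analysis plan, slightly slower fitting and possibly wider intervals. No new data are needed.
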